13.2.4 Hospitalization Prior to the Follow-Up Visit

An assessment of hospitalization (defined as readmission to the hospital if previously hospitalized on or after study drug initiation [Day 1], or initial hospital admission (if not previously hospitalized) for any reason between the initiation of study drug (Day 1) and FU will be made programmatically based on information collected in the eCRF.

For the purposes of this secondary efficacy assessment, “hospital admission” is defined as inpatient admission for at least 24 h in an acute care facility (including inpatient hospital ward or emergency room); in contrast, admission to nursing homes, assisted living facilities, rehabilitation units, or acute care facilities (hospital wards or emergency rooms) for less than 24 h is not considered a formal hospital admission. The assessment of hospitalization within 30 days of study drug initiation is defined in [Table 13.2.4-1](#).

Of note, adverse events that lead to readmission or new admission to the hospital will meet SAE criteria, as defined in [Section 14.1.4](#).

Table 13.2.4-1 Hospitalization Prior to the Follow-Up Visit

Outcome	Definition
Hospitalization Prior to FU	Meets any of the following criteria: 
 • Hospital readmission for any reason between Day 1 and FU Visit, if previously hospitalized and discharged • Initial hospital admission for any reason between Day 2 and FU Visit, if not previously hospitalized on Day 1

Table 13.2.4-1 Hospitalization Prior to the Follow-Up Visit

Outcome	Definition
No Hospitalization Prior to FU	Does not meet the criteria for hospitalization within 30 days of study drug initiation as defined above, or till FU whichever is earlier.
Indeterminate	Study data are missing for evaluation of efficacy at FU Visit for any reason, including lost to follow-up.

Abbreviations: FU = Follow-Up

13.3 MICROBIOLOGICAL OUTCOMES

13.3.1 Microbiological Outcomes at TOC

An assessment of by-subject and by-pathogen microbiological response (favorable, unfavorable, or indeterminate) will be made at TOC (Day 15 \pm 3 days) in the micro-ITT and ME populations. Microbiological outcome categories at TOC are defined in [Table 13.3.1-1](#). Favorable microbiological outcomes include eradication or presumed eradication.

The by-subject microbiological outcome at TOC will be determined based on individual outcomes for each baseline pathogen; specifically, for a subject to have a favorable microbiological outcome, the outcome for each baseline pathogen must be favorable (eradicated or presumed eradicated). If the outcome for any pathogen is unfavorable (persistence or presumed persistence), the subject will be considered to have an unfavorable microbiological outcome.

As CABP responds to therapy, obtaining repeated specimens for culture or examination may not be clinically appropriate and/or there may be no respiratory material for culture. However, if study drug is prematurely discontinued due to insufficient effect of study drug (e.g., failure at EOT or TOC, or clinical relapse at any time), an appropriate respiratory specimen and blood should be obtained for culture on the day of discontinuation ([Section 12.6](#)).

Table 13.3.1-1. Microbiological Outcome Categories at TOC

Outcome	Definition
Eradication	Post-baseline respiratory specimen (e.g., respiratory fluid obtained by bronchoalveolar lavage or bronchoscopy; pleural fluid obtained by thoracentesis; or expectorated or induced sputum meeting adequacy criteria) culture or blood culture demonstrates absence of the original baseline pathogen
Presumed eradication	Post-baseline respiratory specimen culture or blood culture was not available and the subject was assessed as a clinical cure at TOC
Persistence	Post-baseline respiratory specimen culture or blood culture demonstrates continued presence of the original baseline pathogen. Note that post-baseline urinary antigen tests for L. pneumophila or S. pneumoniae should not be performed (Section 12.3), and positive post-baseline urinary antigen tests (if performed) will not be considered as persistence.
Presumed persistence	Post-baseline respiratory specimen culture or blood culture was not

	available and the subject was assessed as a clinical failure at EOT or TOC
Indeterminate	Post-baseline respiratory specimen culture or blood culture was not available and the subject's clinical response was assessed as indeterminate

Abbreviations: EOT = End-of-Therapy; TOC = Test-of-Cure.

CABP caused by pathogens first appearing after Screening (emergent infections) will be categorized as either superinfections or new infections as defined in [Table 13.3.1-2](#). Emergent infections will not be considered in the by-subject or by-pathogen microbiological response analyses described above.

Table 13.3.1-2 Emergent Infections

Category	Definition
Superinfection	Isolation of a new pathogen(s) (other than the original CABP pathogen[s]) from an appropriate post-baseline respiratory specimen (e.g., respiratory fluid obtained by bronchoalveolar lavage or bronchoscopy; pleural fluid obtained by thoracentesis; or expectorated or induced sputum meeting adequacy criteria) culture or blood culture, which is accompanied by signs and symptoms of infection requiring alternative systemic antimicrobial therapy during the period up to and including EOT
New infection	Isolation of a new pathogen(s) (other than the original CABP pathogen[s]) from an appropriate post-baseline respiratory specimen culture or blood culture, which is accompanied by signs and symptoms of infection requiring alternative systemic antimicrobial therapy in the time period after EOT (e.g., TOC)

Abbreviations: CABP = community-acquired pneumonia; EOT = End of Treatment; TOC = Test-of-Cure.

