^lAt Screening, local laboratory evaluations required for assessing subject eligibility include serum transaminase (ALT and AST) and total bilirubin levels, serum creatinine and BUN (or urea), peripheral WBC count, absolute neutrophil count, coagulation, and immature neutrophil percentage. Blood will be collected for central laboratory testing at the Screening, Day 5, EOT and TOC visits (including serum β -HCG in females; full list of central laboratory tests available in [Appendix IV](#)); blood will also be collected for central laboratory testing at FU in subjects with clinically significant laboratory abnormalities noted at or after the TOC visit.

^mCollect blood for acute (Screening) and convalescent (TOC) atypical pathogen serology, including *Mycoplasma pneumoniae*, *Chlamydia pneumoniae*, and *Legionella pneumophila*, for central laboratory testing.

ⁿAt Screening, a urine dipstick will be performed locally; if results are abnormal and deemed clinically significant by the Investigator, a urinalysis will be sent to the central laboratory.

^oAt Screening, urine will be tested locally for *Streptococcus pneumoniae* and *Legionella pneumophila* using provided rapid antigen test kits.

^pAt Screening, local laboratory urine or serum pregnancy test (females only) is required to confirm study eligibility. In addition, blood will be collected from all female subjects for serum β -HCG pregnancy test by the central laboratory at the Screening and TOC visits.

^qAt Screening, collection of expectorated sputum or other deep respiratory sample should be attempted in all subjects. Gram stain will be performed on all sputum specimens and quality assessed. Culture will be performed on all adequate sputum samples or deep respiratory specimens. Post-baseline respiratory specimens should be collected as clinically indicated and from subjects who are clinical failures and require alternative antibacterial treatment for CABP ([Section 12.6](#)).

^rTwo sets of blood cultures (each set consists of 1 aerobic and 1 anaerobic blood culture bottle) will also be collected at Screening. Repeat post-baseline blood cultures should be collected on the day that the positive blood culture is detected. If subsequent blood cultures are also positive, repeat the blood cultures as necessary until negative blood cultures are obtained ([Section 12.6](#)).

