12.2 SCREENING BLOOD CULTURES

At Screening, one aerobic blood culture bottle and one anaerobic blood culture bottle from two separate sites for a total of four bottles must be collected for culture (i.e., 1 aerobic and 1 anaerobic bottle from 2 separate venipuncture sites, for a total of 4 bottles).

Either an automated or a manual system can be used for blood and pleural fluid culture methods according to the preference of the local microbiological laboratory performing the testing. Refer to the Microbiology Laboratory Manual for details.

Culture results are to include identification of pathogens to the level of genus and species. Susceptibility testing for nafithromycin will not be available to the local laboratory; MICs will be assessed at the central laboratory. Therefore, decisions related to subject care (e.g., study drug discontinuation) will be based on the evolution of the clinical signs and symptoms of CABP.

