12.5 POST-BASELINE MICROBIOLOGICAL ASSESSMENTS

At any time after the Screening Visit, respiratory specimen and blood cultures should be obtained as clinically indicated. As CABP responds to therapy, obtaining repeated specimens for culture or examination may not be clinically appropriate and/or there may be no material for culture.

If study drug is prematurely discontinued due to insufficient effect of study drug (e.g., failure at EOT or TOC, or clinical relapse at any time), an appropriate respiratory specimen and blood should be obtained for culture on the day of discontinuation; if new antibacterial therapy is administered to treat the current CABP after premature discontinuation of study drug, it is preferred that respiratory specimens and blood be collected for culture after stopping the study drug but before new treatment is started.

Blood cultures should be repeated upon knowledge of a positive result from any previous collection until sterilization is confirmed ([Table 3-1](#)).

Repeat, post-baseline urinary antigen tests for *L. pneumophila* or *S. pneumoniae* should not be performed.

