16.1.3 Microbiological Intent-to-Treat Population (micro-ITT)

The micro-ITT population will include all ITT subjects who have at least one baseline Gram-positive or atypical bacterial pathogen known to cause CABP, including bacterial pathogens identified by respiratory specimen culture (e.g., respiratory fluid obtained by bronchoalveolar lavage or bronchoscopy; pleural fluid obtained by thoracentesis; or expectorated or induced sputum meeting adequacy criteria), blood culture, urinary antigen test (*S. pneumoniae*, *L. pneumophila*), or atypical bacterial serologic response (*M. pneumoniae*, *C. pneumoniae*, *L. pneumophila*). Subjects with sole baseline Gram-negative bacterial infection will be excluded from this population.

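### Table 13.3.1-1 neither ties Eradication to the source positive at baseline nor ranks it against the other categories, so a clinical failure can count as a favorable microbiological response

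*Combined protocol and SAP*

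**What the plan says.** Table 13.3.1-1 (Section 13.3.1) has five categories.

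- **Eradication:** a post-baseline respiratory specimen (sputum must be adequate) "culture or blood culture demonstrates absence of the original baseline pathogen".
- **Persistence:** the same either/or construction, for continued presence of the pathogen. The row adds that "positive post-baseline urinary antigen tests (if performed) will not be considered as persistence".
- **Presumed eradication:** culture not available and clinical cure at TOC.
- **Presumed persistence:** culture not "available and the subject was assessed as a clinical failure at EOT or TOC".
- **Indeterminate:** no culture available, in a subject whose "clinical response was assessed as indeterminate".

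Other sections supply the context.

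- Section 16.1.3 admits subjects to micro-ITT on culture, a urinary antigen test "or atypical bacterial serologic response".
- Section 12.2 makes screening blood cultures mandatory: one aerobic and one anaerobic bottle "from two separate sites for a total of four bottles must be collected for culture".
- Sections 12.5 and 13.3.1 ask for both a respiratory specimen and blood when study drug is stopped for insufficient effect, but accept that there may be no respiratory material to culture.
- The by-subject rule in Section 13.3.1 lets an unfavorable pathogen dominate. It ranks across pathogens, not across conflicting cultures of one pathogen.
- Section 16.2.3.2 repeats the categories and counts eradication and presumed eradication as favorable. It adds no rule on source or priority.

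**The concern.** A negative culture is evidence of eradication only if that source previously grew the organism. Without that link, a specimen that was already negative at screening can turn a clinical failure into a favorable microbiological response. Without a ranking, some ordinary results satisfy two rows, one favorable and one unfavorable, and two programmers could produce different tables from the same data.

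By-subject and by-pathogen response at TOC are listed secondary endpoints in micro-ITT and ME (Section 13.1), and Section 16.2.1 says the trial is meant to inform Phase 3 design. Source mismatch alone changes the favorable count only through failures and indeterminates. A clinical cure with no positive culture would be presumed eradicated anyway. Any error from mismatch is therefore in the favorable direction.

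**Working it through.** The documents give no figure for the microbiological endpoint, so there is nothing to reproduce. The check applies the table literally to a clinical failure.

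**Inputs.** Post-baseline respiratory and blood results are each negative, positive for the baseline pathogen, or absent, giving 3 × 3 = 9 pairs. The phrase on culture not being available has two readings. Narrow: neither culture exists. Wide: at least one is missing. E = Eradication, P = Persistence, PP = Presumed persistence.

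| Respiratory | Blood | Narrow | Wide |
|---|---|---|---|
| neg | neg | E | E |
| neg | absent | E | E and PP |
| absent | neg | E | E and PP |
| neg | pos | E and P | E and P |
| pos | neg | E and P | E and P |
| pos | pos | P | P |
| pos | absent | P | P and PP |
| absent | pos | P | P and PP |
| absent | absent | PP | PP |

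The baseline source does not enter this table, and that is the defect. Adding it as respiratory only, blood only, both, or antigen/serology only gives 4 × 9 = 36 patterns.

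- **Narrow:** 4 × 3 = 12 patterns are E alone. In 5 every baseline-positive source was re-cultured and negative (2 + 2 + 1 + 0). In 5 no source that grew the pathogen was re-cultured (1 + 1 + 0 + 3). In 2 only one of two positive sources was re-cultured. A further 4 × 2 = 8 meet E and P, 12 are P and 4 are PP.
- **Wide:** 4 × 1 = 4 patterns are E alone, and 3 of these are source-matched. The fourth is antigen/serology only with both cultures negative. The other 4 unmatched and 2 partial patterns become E and PP.

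These counts map the wording. They are not frequencies.

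**Applied to subjects**

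1. *Antigen or serology only, clinical failure, both cultures negative.* E alone on either reading, hence favorable, although no culture grew the pathogen at baseline.
2. *Sputum-only pathogen, clinical failure, no adequate repeat sputum, blood negative.* Screening blood was mandatory, so blood did not grow the pathogen then either and the negative shows no change. E on the narrow reading, E and PP on the wide one.
3. *Positive sputum, negative blood.* E and P on both readings.
4. *Clinically indeterminate, otherwise as 1 or 2.* E by the same route, because the Indeterminate row also requires culture not to be available. In case 2 the wide reading gives E and Indeterminate together.

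**Proposed rule, clinical failure.** Respiratory only: E 2, P 5, PP 2. Blood only: E 2, P 5, PP 2. Both: E 1, P 5, PP 3. Antigen/serology only: E 0, P 5, PP 4. The totals are 5 + 20 + 11 = 36, with one category per pattern.

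**Scale.** With n subjects in an arm's micro-ITT, one reclassified subject moves the favorable rate by 100/n percentage points. The documents do not give n. It cannot exceed the roughly 75 randomized per arm, so the shift is at least about 100/75 = 1.3 points per subject.

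**The case against.** The strongest reply is that sensible readers would settle most of this. Continued growth in adequate sputum is naturally Persistence whatever the blood shows. The endpoint is descriptive, Section 16.2.3.2 plans no statistical comparison for microbiological response, and the same rule applies to every arm. All categories are to be tabulated and individual data listed. Section 16.2 promises a comprehensive SAP before lock, and such derivations often sit there.

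Much of that limits the point, and several stronger inferences do not hold.

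- A reader might infer that the sputum-only failure with negative blood is definitely Eradication. That needs the narrow reading; on the wide one the score is undefined.
- A reader might infer that a positive repeat blood culture later cleared is scored both ways. The outcome is assessed at TOC, and Table 3-1 directs: "If subsequent blood cultures are also positive, repeat the blood cultures as necessary until negative blood cultures are obtained". Clearance is the expected course, so calling it Persistence is strained.
- A reader might extend the indeterminate case to ME. CE requires a cure or failure at TOC, or earlier failure at EOT (Section 16.1.4), and Section 16.2.3.2 says ME has no indeterminates.
- Eradication in a clinical failure with a negative culture from the matching source is an acceptable choice.
- The pattern counts are unweighted, and some depart from the planned sampling, such as bacteremia with no repeat blood culture. They cannot be read as an error rate.

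What stands is the antigen/serology case, which neither reading rescues, and the missing priority. The category table would not show which source was cultured. The protocol does not refer this rule to the SAP.

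**Conclusion.** The point holds as a defect in a stated rule. On either reading, a clinical failure identified only by antigen or serology is favorable when both respiratory and blood cultures are negative. Missing sputum with negative blood is either favorable or doubly classified, and positive sputum with negative blood is doubly classified. In micro-ITT, though not ME, a clinically indeterminate subject can become favorable the same way.

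The number of subjects affected cannot be derived, because micro-ITT size and culture frequencies are not given. The documents do not support a claim that the reported rates will be materially wrong, that one arm is favored, or that the Day 4 primary endpoint is affected. The conclusion assumes that no unseen SAP text or laboratory manual supplies the missing rule. It should be fixed before database lock, with medium confidence.

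**What to change.** Put the following in the SAP derivation before database lock, and align Table 13.3.1-1 at the next amendment.

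- (a) For each source, respiratory and blood, the latest available post-baseline culture up to TOC governs, whether or not that source was positive at baseline.
- (b) If the governing culture from any source grows the baseline pathogen, classify as Persistence, which overrides all other categories. An earlier positive later cleared in the same source does not count.
- (c) Otherwise, Eradication requires a negative governing culture from every source that was culture-positive for that pathogen at baseline.
- (d) Otherwise, treat culture as not available and assign presumed eradication, presumed persistence or indeterminate by clinical outcome. This includes a baseline-positive source that was not re-cultured and a pathogen identified only by antigen or serology.

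Cultures taken after a new antibacterial is started should still be able to count as Persistence. Section 12.5 states timing only as a preference: "it is preferred that respiratory specimens and blood be collected for culture after stopping the study drug but before new treatment is started". For a clinical failure, a negative culture taken only after that start may be flagged in the listing.

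The cost is programming and wording. No new samples are needed, but the table change needs the approvals in Sections 17.1 and 18.4. Favorable rates may be slightly lower, and some results move from documented to presumed categories.

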9.7 GUIDANCE TO INVESTIGATORS ON WHEN TO END STUDY DRUG THERAPY

The duration of study drug in this study is a fixed 7-day course in all three Treatment Arms; therefore, subjects who are improving clinically will receive no less or no more than 7 days of the study treatment regimen. At Day 7 (EOT), an assessment of clinical outcome will be performed by the Investigator. A subject will be determined as a clinical cure at EOT if the subject is alive and the infection is sufficiently resolved such that further antibacterial therapy is not needed ([Section 13.2.2](#)). Note that subjects with CABP may have some residual findings related to infection (i.e., cough) requiring non-antibiotic ancillary treatment (e.g., expectorant) at EOT and still meet criteria for clinical cure.

If additional antibacterial therapy is required for the index CABP (e.g., progressively worsening CABP between Day 1 and Day 7, or gradually improving CABP that requires additional antibacterial therapy beyond 7 days), study drug should be discontinued, the subject will be deemed a clinical failure on the day of study drug discontinuation, and open-label antibacterial therapy will be started at the discretion of the Investigator. Administration of blinded study drug will not be allowed beyond Day 7. In cases of premature discontinuation of study drug, subjects should not be discontinued from the study itself; subjects should remain in the study and undergo all scheduled assessments at EOT, TOC and FU ([Section 11.0](#)).

The Investigator may use culture and susceptibility results from the local microbiology laboratory to help guide therapy; however, decisions to continue or discontinue study drug should be based on clinical response rather than susceptibility results (as nafithromycin susceptibility testing is not available at the local site). If the index CABP is caused by a microorganism that is not susceptible to fluoroquinolones, macrolides, or ketolides in vitro, the decision to continue or discontinue study treatment should be based on the subject's clinical course and the Investigator's clinical judgment. These cases should be discussed with the Medical Monitor prior to prematurely discontinuing study drug, and the rationale for this decision should be recorded in the source documents.

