16.1.4 Clinically-Evaluable Population (CE)

The CE population will include all ITT subjects who follow important components of the trial. Sufficient information regarding the clinical course of CABP must be available to determine the subject's clinical outcome at TOC, and the subject must not have confounding factors that interfere with the assessment of that outcome.

In order to be included in the CE population, subjects must meet all of the following criteria:

- Meet the clinical disease criteria for CABP as described in Inclusion Criterion #3 (Inclusion Criteria 3a–3e; [Section 9.2](#))
- Receive at least 1 dose of study drug
- Do not receive non-study, potentially-effective, systemic antibacterial therapy between Day 1 and TOC (except in cases of treatment failure)
- Have an Investigator-determined clinical response of clinical cure or clinical failure at TOC (unless determined to be a prior clinical failure at EOT)
- Receive at least 80% of the intended doses of study drug therapy

- Receive at least 48 h of study drug therapy in order to be considered an evaluable clinical failure and at least 72 h of study drug therapy in order to be considered an evaluable clinical success

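### Table 13.3.1-1 scores a clinical failure as Eradication when the only post-baseline culture is a negative one taken after rescue antibacterials started

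*Combined protocol and SAP*

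**What the plan says.** Section 13.3.1, Table 13.3.1-1, gives the scoring. Eradication requires a post-baseline respiratory specimen "culture or blood culture demonstrates absence of the original baseline pathogen". The row mentions neither the date of the culture, nor rescue therapy, nor the clinical outcome. The text above the table states: "Favorable microbiological outcomes include eradication or presumed eradication". Presumed persistence applies when a post-baseline culture was not "available and the subject was assessed as a clinical failure at EOT or TOC". Section 16.2.3.2 repeats which categories are favorable and unfavorable and adds no condition on rescue.

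Three other places bear on when cultures are taken:

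- Section 13.3.1, like Section 12.5, says that if study drug is stopped for insufficient effect, "an appropriate respiratory specimen and blood should be obtained for culture on the day of discontinuation".
- Section 12.5 adds that, where new antibacterial therapy follows, "it is preferred that respiratory specimens and blood be collected for culture after stopping the study drug but before new treatment is started".
- Section 12.5 also says: "Blood cultures should be repeated upon knowledge of a positive result from any previous collection until sterilization is confirmed".

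On subjects who need more treatment, Section 9.7 says that study drug is stopped, the subject is a clinical failure, and "open-label antibacterial therapy will be started at the discretion of the Investigator". The subject stays in the study for the EOT, TOC and FU assessments. In Section 16.1.4, the clinically evaluable criterion that bars non-study antibacterials exempts treatment failures. A separate criterion requires at least 80% of intended doses.

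**The concern.** A microbiological response is meant to describe what the study drug did to the baseline pathogen. A negative culture taken while the subject is on another active drug cannot separate the two drugs. The table nevertheless lets that culture support Eradication.

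The result is also internally inconsistent. Where there is no culture, the protocol presumes that a clinical failure still carries the pathogen. It drops that presumption once a culture exists, even if the culture was taken under rescue therapy. Elsewhere rescue counts against the study drug: it is non-response at Day 4 (Section 13.2.1) and, for the listed reasons, clinical failure at EOT or TOC (Section 13.2.2).

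At stake is the by-subject and by-pathogen microbiological response at TOC, a secondary endpoint in micro-ITT and ME. The error can only raise the favorable rate. The Day 4 primary endpoint and the clinical outcomes are not touched.

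**Working it through.** **The plan's own figure.** The plan gives no precision or expected rate for microbiological response. Its only such figure, in Section 16.2.1, is a 95% interval of 66.9% to 86.7% for a 78% Day 4 response with 75 subjects per arm. The Clopper-Pearson limits are the 0.025 quantile of Beta(x, n − x + 1) and the 0.975 quantile of Beta(x + 1, n − x). With x = 0.78 × 75 = 58.5 and n = 75 they are 66.94% and 86.75%, so the figure reproduces. This point does not depend on it.

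**Tracing the rule.** Take clinical failures, all given rescue therapy, who differ only in their post-baseline cultures:

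| Post-baseline cultures | Row met in Table 13.3.1-1 | Result |
|---|---|---|
| None | Presumed persistence | Unfavorable |
| One, negative, taken after rescue started | Eradication | Favorable |
| Positive before rescue, negative after | Persistence and Eradication both met | Not settled; no precedence given |
| Negative before rescue | Eradication | Favorable, and attributable to study drug |

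The second line is the error. It follows directly from the text, because the not-available condition removes that subject from presumed persistence.

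**Is there a scoring safeguard elsewhere?**

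- Sections 12.5 and 13.3.1 say when to collect cultures, not which cultures count.
- Section 13.2.2 carries failure forward, but for clinical outcome only.
- Section 16.2.3.2 adds nothing on rescue.

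**Can the case arise?** Yes. Failures remain in the study (Section 9.7). Table 3-1, footnote q, singles out failures who need alternative treatment for respiratory re-culture. Culture before new treatment is only a preference. A subject who misses the discontinuation-day culture, or has it after rescue began, and is then culture-negative, falls in the second line.

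**Which populations?** Micro-ITT (Section 16.1.3) has no criterion on rescue or dosing, so all such subjects count. ME requires the CE criteria as well (Section 16.1.5). If intended doses means the 7-day course, 0.80 × 7 = 5.6, so 6 of 7 doses are needed. A failure switched earlier would then be outside CE and ME.

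**Size per subject.** The documents give no micro-ITT size, failure rate or count of post-rescue cultures. Assume micro-ITT is 20% to 50% of 75, that is 15 to 38 subjects per arm (37.5 rounded). One subject moved from unfavorable to favorable shifts the rate by 100/n points:

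- n = 15: 100/15 = 6.7 points
- n = 30: 100/30 = 3.3 points
- n = 38: 100/38 = 2.6 points

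As an illustration with n = 30, 24 favorable is 80.0% (Clopper-Pearson 61.4% to 92.3%). Two rescored subjects make it 26/30 = 86.7% (69.3% to 96.2%).

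**The case against.** The strongest reply is that the case will be uncommon. Cultures are requested on the day study drug is stopped for insufficient effect, and later respiratory cultures are taken only if clinically indicated. This stands as a limit on frequency. It does not change how an affected subject is scored.

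A reader might infer that bacteremic failures will normally end as Eradication, because blood cultures are repeated until negative. The documents do not support that. The first repeat is drawn on the day the positive is detected (Table 3-1, footnote r), and Section 9.4.1.2 encourages at least 48 h of study drug before stopping, so that repeat will usually precede rescue. If it is negative, clearance was shown on study drug and no further repeat is prompted. If it is positive, the subject also meets Persistence, and the gap is then the missing precedence between categories.

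A reader might also infer that rescued failures stay in ME through the treatment-failure exemption. That exemption covers only one criterion. The 80% criterion still applies and probably removes many subjects rescued early.

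Finally, the trial is descriptive. Section 16.2.3.2 plans no statistical comparison of microbiological response and requires a table of all response categories and individual listings. Clinical outcome at TOC is also reported in micro-ITT, so a clinical failure scored Eradication could be found on review. This lowers the consequence but leaves the reported rate wrong. Section 16.2 defers to a comprehensive SAP, but the text available, including Section 16.2.3.2, contains no rule that closes the gap.

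**Conclusion.** The rule is wrong as written, by omission and in a limited set of cases. A clinical failure whose sole available post-baseline culture is a negative one taken after rescue started is scored favorable. The bias is upward, mainly in micro-ITT, and in ME only for failures who also meet the 80% criterion.

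The total size cannot be computed from the documents. Per rescored subject it is about 6.7 to 2.6 points in that arm's favorable rate, assuming 15 to 38 micro-ITT subjects per arm.

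A reader might go further and estimate an overall bias, for example 5 to 10 points from failure rates of 10% to 20% with half of the failures rescored. Nothing in the documents supports a share of one half, and the discontinuation-day culture argues against assuming it. Nor can one say that the rule favors a particular arm. The shift would be larger in the arm with more failures only if the affected share were similar across arms, which is unknown.

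The point is worth correcting because Section 16.2.1 says that the data are to inform the design of later studies.

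**What to change.** State in Table 13.3.1-1 and Section 16.2.3.2 that:

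- only cultures collected before the first dose of non-study, potentially effective systemic antibacterial therapy can support Eradication;
- a negative culture collected later is treated as not available, so that a clinical failure becomes presumed persistence;
- a culture collected on the same day as the first such dose counts as pre-rescue unless recorded times show otherwise;
- post-rescue cultures are flagged in the listing.

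The existing rows then handle every case. A cure becomes presumed eradication and an indeterminate subject stays indeterminate. A subject positive before rescue and negative after it is left with Persistence alone. A negative culture taken before rescue still counts as Eradication.

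The cost is a few lines of text and a date comparison in programming. Section 10.3 already requires concomitant systemic antimicrobials to be documented. The same-day convention is needed because culture and rescue may fall on the same day, and the documents do not say that clock times are recorded for both. The favorable rate may be slightly lower. The change concerns scoring only, leaves patient care as it is, and should be made before database lock and unblinding.
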